Descriptive statistics (N, mean, standard deviation, median, minimum, and maximum) will be presented for continuous variables. Geometric means and coefficient of variation will also be presented for PK data. Frequency distributions (counts and associated percentages) will be presented for categorical variables. Median, 25th and 75th percentiles and confidence intervals (Cls) will be presented for time-to-event data. Unless specified otherwise, CIs will be presented as 95% Cls.

The study is descriptive in nature and is not powered for a confirmatory statistical goal or objective. Formal hypothesis testing will not be done, and no adjustment for multiple comparisons will be used.

Individual patient data listings will be provided to support summary tables.

Version: Amendment 4 Date: 31 Mar 2020

The effects of noncompliance, treatment discontinuations, premature study withdrawals, subsequent therapies, and covariates will be assessed to

determine the impact on the general applicability of results from this study.

Protocol Number: NVGN-0084-201

IND Number: 112,608

Analysis of Clinical Benefit:

The Kaplan-Meier method will be used to describe and present PFS and any other time-to-event endpoints (OS, TTP, etc). Median PFS will be presented with 95% CI, 25th and 75th percentiles and minimum and maximum values. Kaplan-Meier estimates of PFS at 6, 9, and 12 months will also be presented with 95% CIs.

The primary analysis of time to event endpoints (OS, TTP, and PFS) from Stage 2 will be based on the mITT and/or PP as appropriate.

For exploratory analyses, DCR will be compared between treatment arms using Fisher's exact test. The difference in the proportion of responders and corresponding 95% CI (based on the Hauck-Anderson approach) will also be displayed. The blinded central review disease response assessments will be used as the primary measure for analysis, and the Investigator disease response assessments will be used as supportive measures for analysis.

Safety Analysis:

All safety analyses will be conducted in the safety population.

AEs will be coded according to the Medical Dictionary for Regulatory Activities (MedDRA). The severity of AEs will be graded according to the United States NCI CTCAE, version 4.03.

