The randomized clinical trial EORTC (European Organization for Research and Treatment of Cancer) 26981-22981/NCIC CTG (National Cancer Institute of Canada Clinical Trials Group) CE.3 established TMZ as part of the standard of care for GBM. It has long been established, however, that GBM patients with a methylated MGMT promoter (epigenetically silenced) are most likely to benefit from the addition of TMZ as an adjuvant therapy following combined XRT/TMZ (Hegi, Diserens et al. 2005, Stupp, Hegi et al. 2009). Patients with unmethylated MGMT promoter tumors derived only a 1-month improvement in median survival, and absolute increases in 2- and 5-year survival of approximately 13% and 8%, respectively (Hegi, Diserens et al. 2005, Stupp, Hegi et al. 2009). The marginal benefit of combination therapy for the unmethylated population has brought into question the use of combination therapy as an absolute standard, particularly in the clinical trial setting (Alexander and Cloughesy 2017). While the Stupp regimen (Stupp, Mason et al. 2005) has been the standard of care in adjuvant and newly diagnosed GBM for over a decade, data have shown that OS in the two-thirds of patients who have unmethylated MGMT is only 12.7 months, and PFS is only 5.3 months (Hegi, Diserens et al. 2005).

Patients with unmethylated MGMT, therefore, represent the patient group with the highest unmet need requiring new treatment options; a role that GDC-0084 may fulfil given that its action is independent of the MGMT promoter status of GBM tumors.

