4.5 Endpoints

4.5.1 **Primary Endpoint**

The primary endpoint of this study is safety-related and is the occurrence of DLTs during the study.

Protocol Number: NVGN-0084-201

Secondary Endpoints 4.5.2

Secondary endpoints are related to both, safety and clinical benefit as listed below.

Secondary Safety Endpoints:

- Treatment-emergent AEs (TEAEs), Grade 3-5 TEAEs, serious adverse events (SAEs), fatal AEs, and TEAEs leading to GDC 0084 discontinuation or study withdrawal;
- Treatment-emergent Grade 3/4 clinical laboratory abnormalities;
- Changes and shifts from baseline in clinical laboratory, vital signs, and ECG parameters;
- Change from baseline in corticosteroid use;
- Change from baseline in LVEF;
- Change from baseline in KPS;
- Concomitant medication use;
- Adherence to the dosing regimen.

Secondary Endpoints of Clinical Benefit:

- PFS measured from first dose in the dose-escalation portion (Stage 1) or from randomization in the cohort expansion portion of the study (Stage 2) to disease progression (RANO criteria) or death due to any cause:
- OS measured from first dose in the dose-escalation portion (Stage 1) or from randomization in the cohort expansion portion of the study (Stage 2) to death due to any cause;
- TTP measured from first dose in the dose-escalation portion (Stage 1) or from randomization in the cohort expansion portion of the study (Stage 2) to date of earliest disease progression according to RANO criteria.

4.5.3 **Exploratory Endpoints**

Exploratory endpoints in this study are:

- PFS measured from first dose in the dose-escalation portion (Stage 1) or from randomization in the cohort expansion portion of the study (Stage 2) to disease progression (modified RANO criteria) or death due to any cause:
- PK parameters including area under the curve from time 0 to last measurable time point (AUC_{0-last}) and/or area under the curve from time 0 to infinity (AUC_{0-inf}), maximum concentration (C_{max}), minimum concentration (C_{min}), time to reach C_{max} (T_{max}), t_{1/2}, apparent total clearance of the drug from plasma after oral administration (CL/F), and accumulation ratio for C_{max} and AUC (fed and fasted);
- Change in FDG-PET uptake in tumor and normal brain tissue (defined as normal brain tissue with similar cell type to tissue surrounding tumor) in response to GDC-0084 in patients with measurable disease:

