PFS is defined as the time in months from start date and/or date of disease diagnosis until disease progression or death due to any cause. Patients without disease progression or death will be censored at the last evaluable radiographic assessment. Patients with no post-dose radiographic assessment will be censored at their start date (Day 1). The primary analysis of PFS will be conducted in the SAF for Stage 1 and the mITT for Stage 2. Analyses of PFS may be repeated in the PP.

The Kaplan-Meier method will be used to describe and present PFS. Median PFS will be presented with 95% CI, 25th and 75th percentiles and minimum and maximum values. Kaplan-Meier estimates of PFS at 6, 9, and 12 months will also be presented with 95% CIs. PFS will also be displayed graphically using Kaplan-Meier estimates.

For Stage 2, differences between treatment arms will be tested using a two-sided log rank test. Stratified hazard ratio (HR) estimates of the treatment comparisons with associated 95% CIs will be estimated from a Cox regression model.

OS is defined as the time in months from start date and/or disease diagnosis until death due to any cause. Patients who are alive at the time of analysis will be censored at the date last known to be alive. The primary analysis of PFS will be conducted in the SAF for Stage 1 and the ITT for Stage 2. Analyses of OS may be repeated in the mITT and/or PP.

TTP is defined as the time in months from start date and/or until disease progression . Patients without disease progression will be censored at the last evaluable radiographic assessment. Patients with no post-dose radiographic assessment will be censored at their start date (Day 1).

Analyses of OS and TTP will be performed using the same methods as described for PFS.

Post-hoc stratification/analysis factors may include disease progression (post-surgery at time of baseline visit) and baseline KPS.

Version: Amendment 4 Date: 31 Mar 2020

Protocol Number: NVGN-0084-201

IND Number: 112.608

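### TTP censors deaths without progression and uses Kaplan-Meier, so one minus the curve overstates the probability of progression; add a cumulative incidence estimate

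*Combined protocol and SAP*

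**What the plan says.** Section 4.5.2 defines TTP as running "to date of earliest disease progression according to RANO criteria". The PFS definition in section 6.3.4 runs "until disease progression or death due to any cause", so the two endpoints differ in whether death counts.

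For TTP, section 6.3.4 then says: "Patients without disease progression will be censored at the last evaluable radiographic assessment". There is no separate rule for a patient who dies without progression. Someone with no scan after dosing is censored at Day 1.

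On method, section 6.3.4 says: "Analyses of OS and TTP will be performed using the same methods as described for PFS". The synopsis (section 2.1) names the estimator: "The Kaplan-Meier method will be used to describe and present PFS and any other time-to-event endpoints (OS, TTP, etc". The landmark times are stated for PFS: "Kaplan-Meier estimates of PFS at 6, 9, and 12 months will also be presented with 95% CIs". They reach TTP only by implication, through the sentence that carries the PFS methods over. No cumulative incidence or competing-risk estimate is named for any endpoint.

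For the analysis population, the synopsis says that the time-to-event endpoints "from Stage 2 will be based on the mITT and/or PP as appropriate". Section 6.3.1 limits mITT to treated, eligible patients who have evaluable tumor data after baseline.

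**The concern.** Kaplan-Meier treats a censored patient as someone who goes on to progress at the same rate as those still under observation. That is reasonable for a patient who is alive with no further scan. It is not reasonable for a patient who has died, because progression can no longer occur. With such deaths censored, 1-KM estimates how many patients would progress if nobody died first, and that is higher than the share who actually progress.

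TTP is a named secondary endpoint of clinical benefit, and in a descriptive study the estimate itself is what gets reported. The design leaves room for deaths without documented progression. Table 1 schedules no MRI in long-term follow-up, which may be by telephone. Tumor data count only until the next anti-cancer therapy starts. For Stage 2, the blinded central reading is the primary measure.

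**Working it through.** The documents give no TTP rate, TTP event count or Stage 2 sample-size calculation, so there is no planned figure to reproduce. The check asks how far 1-KM lies from the cumulative incidence of progression (CIF).

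**Inputs**
- Median time to first event, 5.3 months. Section 3.2 says that "OS in the two-thirds of patients who have unmethylated MGMT is only 12.7 months, and PFS is only 5.3 months". This is historical, not a planning assumption of this trial, so 4 and 7 months are also tried.
- Share p of first events that are deaths without progression. The documents do not give it. Assumed 5% to 30%.
- Scans every 8 weeks (section 4.6.3). Stage 2 has 20 patients, 10 per arm (section 4.3.1).
- Exponential times (assumed).

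**Continuous time, all treated patients**

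Total hazard L = ln 2 / 5.3 = 0.1308 per month.
- 1-KM at 12 months = 1 − exp(−L(1 − p) × 12)
- CIF at 12 months = (1 − p)(1 − exp(−L × 12))

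For p = 20%: 1-KM = 1 − exp(−0.1308 × 0.8 × 12) = 71.5%. CIF = 0.8 × (1 − 0.208) = 63.3%. The gap is 8.2 points.

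**With 8-weekly scans and the mITT exclusion**

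Date progression at the next scan and censor deaths at the previous one. The interval is 56/30.44 = 1.84 months, so S = exp(−0.1308 × 1.84) = 0.786, and six scans fall within 12 months.
- 1-KM = 1 − [S / (1 − p(1 − S))]^6. This is the same with or without the mITT exclusion, because a death before the first scan would otherwise be censored at Day 1 and never enter a risk set.
- CIF, all treated = (1 − p)(1 − S^6)
- CIF, mITT = the line above divided by 1 − p(1 − S), the fraction who do not die before the first scan

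For p = 20%: 1 − p(1 − S) = 0.957, so 1-KM = 69.3%. CIF is 61.1% in all treated patients (gap 8.2) and 61.1/0.957 = 63.8% in mITT (gap 5.5).

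| p | 1-KM, continuous | CIF, continuous | Gap, all treated | Gap, mITT with scans |
|---|---|---|---|---|
| 5% | 77.5% | 75.2% | 2.3 | 1.5 |
| 10% | 75.6% | 71.3% | 4.4 | 2.9 |
| 20% | 71.5% | 63.3% | 8.2 | 5.5 |
| 30% | 66.7% | 55.4% | 11.2 | 7.7 |

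Gaps are in percentage points, taken before rounding. Simulation of the scan schedule gave 2.3, 4.4, 8.2 and 11.3 points for all treated patients, and 1.4, 2.9, 5.5 and 7.7 for mITT.

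**Other medians, p from 5% to 30%**
- 7 months: 1.6 to 7.8 points in all treated patients, 1.1 to 5.4 in mITT.
- 4 months: 3.0 to 15.4 in all treated patients, 1.9 to 10.4 in mITT.

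**Earlier landmarks** (5.3 months, p = 20%, all treated): 3.1 points at 6 months and 5.7 at 9 months.

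**Against sampling error**

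In simulated trials of 20 patients, the standard deviation of the 12-month estimate was 10.2 points at p = 10% and 12.4 at p = 30%. The 95% half-widths are 1.96 × 10.2 = 20 and 1.96 × 12.4 = 24 points. With 10 per arm they are about 28 and 35. Expected deaths without progression by month 12 among 20 patients are 20 × p × (1 − 0.208), or 1.6 at p = 10% and 4.8 at p = 30%.

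**The case against.** The strongest reply is that this is a matter of definition and does little harm. Leaving death out of TTP is legitimate. PFS, which counts death, is reported beside it by the same methods, and so is OS. Log-rank and Cox with deaths censored remain valid for the cause-specific hazard. The study is descriptive and unpowered, its primary endpoint is dose-limiting toxicity, and no decision rule uses TTP. The Stage 2 mITT drops deaths before the first scan, which shrinks the gap. All of this stands, and it keeps the severity low. It does not make 1-KM the probability of progression: deaths after the first scan are still censored, and the confidence interval around the Kaplan-Meier estimate does not allow for the shift.

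A second reply is that a separate SAP may settle the matter. Section 6.3 leaves data-handling detail to that document. However, section 6.3.4 defers only the rules for confirming progression, their effect on the calculations, and the related sensitivity analyses. It does not defer the choice of estimator or the handling of deaths. A fuller rule elsewhere cannot be excluded.

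A reader might infer that the planned analysis flatters the drug. The documents do not support that. Against cumulative incidence, the planned analysis makes the drug look worse: at p = 20% the Kaplan-Meier median is ln 2 / (0.8 × 0.1308) = 6.6 months, while cumulative incidence reaches 50% at −ln(1 − 0.5/0.8) / 0.1308 = 7.5 months. Benefit would look inflated only if the TTP curve were misread as the proportion alive without progression, and the plan reports that separately as PFS.

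**Conclusion.** The point holds as a cheap improvement of low severity. As written, deaths without progression are censored for TTP and Kaplan-Meier is applied, so 1-KM overstates the probability of RANO progression.

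The size is conditional. With exponential times, a 5.3-month median and death shares of 5% to 30%, the 12-month overstatement is about 2 to 11 points in all treated patients and about 1.4 to 8 in the Stage 2 mITT. Letting the median vary from 4 to 7 months widens the range to about 1 to 15 points. No single figure can be called the error of this trial, because the documents give neither the death share nor a planning median. The gap lies within sampling error at this sample size, but it always has the same sign and more patients would not remove it.

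It would be wrong to conclude that the TTP definition or the arm comparisons are faulty. The issue is the estimator of the progression probability and how it is labelled.

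**What to change.** In section 6.3.4 and the SAP, separate TTP from the sentence that gives it the PFS methods, and state:
- TTP is summarised as the cumulative incidence of RANO progression (Aalen-Johansen), with death without progression as a competing event at its date of death and 95% CIs at 6, 9 and 12 months.
- The cumulative incidence of death without progression is shown beside it.
- Censoring at the last evaluable scan applies to patients who are alive without progression.
- If the Kaplan-Meier TTP curve is kept for comparison with published values, it is labelled cause-specific, with a note that its complement is not the proportion who progress.

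The log-rank and Cox analyses stay as they are.

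The cost is some wording and one extra analysis in standard software. Dates of death are already collected for OS, so no new data or patients are needed. The downside is that the main TTP figure is less directly comparable with published Kaplan-Meier values, which the labelled curve would cover.

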6.3.6 Pharmacokinetic Analysis

All PK analyses will be conducted on the PK population.

Serum concentrations before and after GDC-0084 administration and PK parameters (AUC_{0-last} and/or AUC_{0-inf}, C_{max} , C_{min} , T_{max} , $t_{1/2}$, CL/F, and accumulation ratio for C_{max} and AUC) will be summarized by dose level (Stage 1) and treatment arm (Stage 2). Individual and mean concentrations vs. time will be displayed graphically.

Non-compartmental analysis will be used to calculate the PK parameters. Further details will be provided in the SAP.

6.3.7 FDG-PET Analysis

All FDG-PET analyses will be conducted on the ITT population in Stage 2.

For Stage 2 only (and patients who have these tests ony), FDG-PET uptake in tumor and normal brain tissue before and following administration of GDC-0084 will be summarized by visit and across treatment arm.

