3.5 Rationale for Conducting this Study

GBM is highly aggressive and patients have limited treatment options. Genetic alterations activating the PI3K pathway are common in patients with GBM (Parsons, Jones et al. 2008). GDC-0084 was designed to efficiently cross the blood-brain barrier with little efflux, providing greater drug exposure in the brain, thus maximizing its ability to target brain cancers such as GBM. A PI3K/mTOR inhibitor with significant brain penetration such as GDC-0084 may provide increased clinical benefit to GBM patients over currently available therapies (which either are not brain penetrant or do not target a key signaling pathway). GDC-0084 has proven to be efficacious in nonclinical models of brain tumors driven by activation of the PI3K pathway. Suppression of downstream factors in this pathway, such as phospho-Akt and phospho-S6, results in arrest of cell division and apoptosis *in vitro* and *in vivo*. Taken together with nonclinical toxicology findings that were generally reversible and consistent with inhibition of the PI3K/mTOR pathway, these *in vitro* and *in vivo* data support the daily and intermittent use of GDC-0084 as a single agent for the treatment of patients with GBM.

GDC-0084 has been studied in a phase 1 clinical trial study (Wen et al, J Clin Oncol 34, 2016; NCT01547546) an open-label, multicenter, dose-escalation study evaluating the safety, tolerability, and PK of GDC-0084, administered orally, once daily, to 47 patients with progressive or recurrent high-grade gliomas. In this population of patients, the AEs and other safety findings were generally consistent with the established Class I phosphoinositide 3-kinase (PI3K) and mammalian target of rapamycin (mTOR) kinase inhibitor class-effects and/or with the disease under study. GDC-0084 is rapidly absorbed and demonstrates linear- and dose-proportional increases in exposure with 7/8 patients dosed at the dose of 45 mg having drug exposures consistent with anti-tumor activity in preclinical models. Fluorodeoxyglucose-positron emission tomography (FDG-PET) scans of tumor brain tissue and normal brain tissue suggest that GDC-0084 crosses the blood brain barrier, with a uniform distribution throughout the brain. The MTD was determined to be 45 mg when dosed once daily.

The current phase 2 clinical development program will investigate the efficacy and safety of GDC-0084 in the treatment of patients with newly diagnosed GBM, with unmethylated MGMT

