3.6.3 Exploratory Objectives

Exploratory objectives in this study are:

- To evaluate and document clinical response assessed as PFS using modified RANO criteria for QD dosing schedule;
- To further characterize the PK parameters of GDC-0084 administered at the MTD;
- To characterize the PK parameters of GDC-0084 when administered to both fasted and fed subjects;
- To assess the distribution of GDC-0084 within the brain by FDG-PET analysis of tumor and normal brain tissue (expansion cohort only);

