Prior to the scheduled FDG injection, patients should fast for at least 4 hours (preferably 6 hours). The blood glucose level should be determined at the time of the FDG-PET scan. Use of anti-hyperglycemic medications, including insulin, immediately prior to the FDG-PET scan is not permitted, as these agents will impact FDG uptake and compromise the interpretability of the FDG-PET scan. Specifically, no short-acting insulin should be administered within 4 hours prior to FDG administration.

Median and mean FDG-PET standard uptake value within the contrast enhancing, measurable target lesion(s), contralateral normal-appearing cortical tissue, and contralateral normal-appearing white matter will be quantified.

4.6.4 **Cardiac Assessment**

Cardiac assessment will be performed by the Investigator and be based on assessment of medical history, physical examination, 12-lead ECG results (including QTc) and evaluation of LVEF by echocardiography (ECHO) or multi-gated scan (MUGA) as well as, as clinically indicated, measurement of troponin T and B-type natriuretic peptide as potential biomarkers of early

Version: Amendment 4 Date: 31 Mar 2020

cardiotoxicity. Cardiology consult may be sought by the Investigator if required to confirm suitability for inclusion in the study.

Protocol Number: NVGN-0084-201

IND Number: 112.608

Except for baseline ECGs at screening, ECGs should be conducted approximately 2 hours post-dose, to coincide with the approximate timing of T_{max} determined in a prior clinical study.

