4.10.1 Hyperglycemia and Metabolic Effects

It is known that PI3K-mTOR pathway inhibitors can affect glucose and/or insulin metabolism, leading to hyperglycemia. Cases of hyperglycemia, including Grade 3 in severity, have been observed in the GDC-0084 single-agent study GO28070. Glucose levels at baseline and during study should be carefully monitored, and appropriate dose delays/dose modifications for managing hyperglycemia should be implemented per protocol quidelines. Patients should be instructed to report symptoms associated with hyperglycemia such as thirst, frequent urination, and blurred vision. Use of oral anti-hyperglycemic agents, such as metformin, for patients experiencing Grade ≥ 2 hyperglycemia may be implemented. Anti-hyperglycemic agents should be used to control severe hyperglycemia per institutional standard of care.

Other metabolic effects known to be associated with mTOR inhibitors include hyperlipidemia. Cases of low-grade hypercholesterolemia and hypertriglyceridemia have been observed in the GDC-0084 single-agent study GO28070. Cholesterol and triglyceride levels should be monitored per protocol guidelines. Use of lipid-lowering therapy for patients experiencing Grade ≥ 2 elevations may be initiated per institutional standard of care and protocol guidelines.

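### The FDG-PET analysis specifies no use of scan-time glucose, so a fall in uptake on GDC-0084 could be partly a systemic glucose effect and be misread as drug distribution in the brain

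*Combined protocol and SAP*

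**What the plan says.** **Objective.** Section 3.6.3 sets the exploratory aim "To assess the distribution of GDC-0084 within the brain by FDG-PET analysis of tumor and normal brain tissue". Section 3.5 already reads the phase 1 FDG-PET data this way: the scans "suggest that GDC-0084 crosses the blood brain barrier, with a uniform distribution throughout the brain".

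**Measure and timing.** Section 4.6.3 quantifies "Median and mean FDG-PET standard uptake value within the contrast enhancing, measurable target lesion(s), contralateral normal-appearing cortical tissue" and contralateral white matter. Scans are taken before the first dose and on Days 3 and 7 of Cycle 1. The same section adds: "The blood glucose level should be determined at the time of the FDG-PET scan".

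**Analysis.** Section 6.3.7 gives a descriptive summary only: "FDG-PET uptake in tumor and normal brain tissue before and following administration of GDC-0084 will be summarized by visit and across treatment arm". It names no glucose adjustment, covariate, threshold or sensitivity analysis. Section 6.3.5 uses glucose for safety tables.

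**Drug and glucose.** Section 4.10.1 states that "PI3K-mTOR pathway inhibitors can affect glucose and/or insulin metabolism, leading to hyperglycemia". The Risk/Benefit Analysis lists hyperglycemia among the most frequent drug-attributed events in phase 1, with a Grade 3 rate of 8.5%.

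**The concern.** FDG is a glucose analogue. If uptake per unit of tissue metabolism falls as plasma glucose rises, a systemic rise in glucose lowers SUV in tumor and normal brain together. That resembles what a drug spread evenly through the brain would produce.

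The design cannot separate the two explanations from SUV alone. Baseline is drug-free and both later scans are on drug, so any drug-induced rise in glucose moves in step with treatment. Both Stage 2 arms receive GDC-0084 and differ only in fed or fasted dosing, so neither is an untreated control. The schedule of assessments (Table 1) has no chemistry on Days 3 and 7, which leaves the scan-time value as the only scheduled glucose at the on-drug scans. The plan gives that value no stated role in the PET analysis.

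At stake is how one stated objective is interpreted. The DLT, MTD, PFS and OS analyses are not affected.

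**Working it through.** **1. The one relevant figure in the documents.** The Risk/Benefit Analysis gives 8.5% related Grade 3 hyperglycemia in 47 patients. 4/47 = 8.51%, so the figure reproduces (exact 95% CI 2.4% to 20.4%). Applied to 20 Stage 2 patients, the expected number is 20 × 4/47 = 1.7, and the chance of at least one is 1 − (43/47)^20 = 83%. This is a rough guide only. The rate pools doses from 2 to 65 mg, covers the whole of phase 1 rather than Days 3 and 7, and omits Grade 1–2 rises, for which no rate is given. PET may also be done in fewer than 20 patients, because it depends on site capability.

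**2. Possible size of the artefact (assumed).** Let r be the relative rise in scan-time glucose from baseline. Let g be the sensitivity of SUV to glucose: 0 is none, 0.5 a square-root law, 1 an inverse law. Neither is in the documents. With tissue metabolism unchanged:

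- change in unadjusted SUV = (1 + r)^(−g) − 1
- change in SUV × glucose / reference = (1 + r)^(1−g) − 1

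| Glucose rise | Version | g = 0 | g = 0.5 | g = 1 |
|---|---|---|---|---|
| 10% | unadjusted | 0% | −4.7% | −9.1% |
| 10% | adjusted | +10.0% | +4.9% | 0% |
| 30% | unadjusted | 0% | −12.3% | −23.1% |
| 30% | adjusted | +30.0% | +14.0% | 0% |
| 50% | unadjusted | 0% | −18.4% | −33.3% |
| 50% | adjusted | +50.0% | +22.5% | 0% |

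Unadjusted SUV can show a false fall. Adjusted SUV can show a false rise when g is below 1. Neither is safe alone.

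**3. Why the pair is informative.** Let m be the true ratio of on-drug to baseline uptake at constant glucose. The unadjusted ratio is m(1 + r)^(−g) and the adjusted ratio is m(1 + r)^(1−g). For r ≥ 0 and g between 0 and 1, the first is at most m and the second at least m, so the two bracket the truth. If both fall, the fall is not explained by glucose within this model, measurement noise aside.

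The price is sensitivity. The adjusted version falls only if the true fall exceeds 1 − (1 + r)^(−(1−g)). For a 30% rise and g = 0.5 this is 1 − 1/1.140 = 12.3%; for g = 0 it is 1 − 1/1.30 = 23.1%. Smaller true effects would be called inconclusive.

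**4. The tumor-to-contralateral ratio.** If glucose acts equally on both tissues, it cancels from the ratio. So does a real drug effect common to both, so the ratio cannot settle whether the drug acts in normal brain.

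**The case against.** Several points on the other side stand.

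- **The SAP may deal with it.** Section 6.3 leaves transformations and data handling to a separate SAP, ranks that document above its own text, and the SAP is not among the documents supplied. Section 6.3.3 promises patient listings and an assessment of covariates, and 6.3.4 allows further exploratory analyses. A reader might infer that glucose is collected and then ignored; the text supports only that the protocol states no use for it in the PET analysis. The gap remains because 6.3.7, unlike the PK section 6.3.6, does not point to the SAP, and none of the general provisions names scan glucose.
- **The artefact is not shown to occur.** A reader might infer that drug-induced hyperglycemia will look like brain penetration. The documents do not say that higher glucose lowers brain FDG uptake, give no size for such an effect, and report no glucose values for Days 3 and 7. The warning in 4.6.3 concerns anti-hyperglycemic agents. The claim is that it could happen.
- **There are safeguards.** Section 4.6.3 requires a fast of at least 4 hours, preferably 6, before FDG, and 4.2.2 excludes diabetic and clinically confirmed prediabetic patients. Both should limit scan-time glucose. Neither removes a rise caused by the drug after baseline.
- **Glucose adjustment has its own bias.** The table shows this, and it rules out making adjusted SUV the sole measure.
- **The endpoint is exploratory.** It is untested and limited to patients with measurable disease at capable sites. That bounds the consequence but does not change the interpretation problem.

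**Conclusion.** The point holds as a limited one. Followed as written, the FDG-PET summary cannot separate a systemic glucose effect from an effect in the brain, and scan-time glucose, which is already collected, would help to do so. For a 30% rise in glucose, the false fall in SUV ranges from 0% to 23%, with 12% under a square-root law. These figures rest on an assumed sensitivity between 0 and 1 and an assumed rise, neither of which is in the documents.

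It would go too far to conclude that a brain effect is disproved or that any observed fall is an artefact. The supported conclusion is that a fall in SUV on its own would be ambiguous, and that reading it as drug distribution goes further than the measure allows. The endpoint in section 4.5.3 is already worded more safely, as a change in uptake in response to the drug.

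**What to change.** In section 6.3.7 or the SAP, before any PET analysis:

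1. Report within-patient percent change from baseline at Days 3 and 7 in both unadjusted SUV and glucose-adjusted SUV (SUV × scan glucose / reference), side by side for each tissue, with neither decisive alone.
2. List scan-time glucose by patient and visit.
3. Describe a fall as a drug effect in brain only when both versions agree, and otherwise call the result inconclusive.
4. Show the tumor-to-contralateral ratio as supplementary only.
5. Describe the result as a pharmacodynamic effect on FDG uptake, in line with section 4.5.3, not as distribution of the drug.

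**Cost.** One derived variable and one listing, from data already collected. Placed in the SAP, items 1 to 4 need no change to the protocol text. Editing 6.3.7 or rewording the objective in 3.6.3 and the synopsis would need a formal amendment with IRB approval under section 10.4. The statistical downside is over-correction when sensitivity is below 1 (+14% for a 30% glucose rise at half sensitivity), which is why both versions are shown. Modest true effects may then be reported as inconclusive.
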